### 3.5.7 Scheduled Visit Procedures

#### Visit 1 (screening, Week -8 pre-surgery)

Potential subjects shall be verified to be candidates for standard cochlear implantation, this screening process may be utilized to determine whether an individual may be appropriate for this study (e.g. motivation, geographical remoteness, willing to commit to protocol requirements, language skills).

Screening may be accomplished during a medical visit, telephone or telemedical consultation, by mail and/or through medical records. Prior to enrollment, all potential subjects shall be presented with the informed-consent form and shall be given the time to read, understand and/or request further information or clarification regarding study requirements and associated risks.

Consent is required once and may be obtained either at this visit or at visit 2.

#### Visit 2 (inclusion, Week -4 pre-surgery)

- Written informed consent: consent is required once and may be obtained either at this visit or at visit 1.
- Subjects will be assigned a single subject identifier (SSID) by the sponsor
- The physician and/or qualified clinician shall verify that the potential subject has appropriate hearing aid settings to be in the best aided condition in accordance with good clinical practice and audiological standards.
- Inclusion/exclusion criteria shall be reviewed to verify the potential subject meets all enrollment requirements
- Demography, medical history, concomitant medications and any potential contra-indications to study inclusion requirements shall be reviewed
- Audiometric evaluations: HINT-Q, HINT-N shall be obtained in the best-aided conditions
- Audiometric evaluations in routine care shall be recorded, if available
- Cochlear implantation scheduling shall be reviewed and confirmed

#### Visit 3 (implantation, Week 0 surgery)

Surgery shall be performed according to conventional cochlear implantation standards and good surgical clinical practice.

- Time of surgery and surgical approach shall be recorded on the CRF
- Objective measures: electrode impedances and ECAP if obtained, shall be recorded
- Complications/adverse effects shall be recorded
- Concomitant medication(s) shall be noted on the CRF

#### Visit 4 (follow-up, Week +2 post surgery)

- Perform clinical examination (general state, scarring, skin-flap assessment,)
- Complications/adverse effects shall be recorded
- Concomitant medication(s) shall be recorded

#### Visit 5 (activation, Month +1)

- Activation and fitting of Neuro CIS shall be performed
- Objective measures: electrode impedances shall be recorded
- Subject will be instructed in the use of Subject's diary
- Complications/adverse effects shall be recorded
- Concomitant medication(s) shall be recorded

**Visit 6 (follow-up, Month +3 post-activation)**

- Audiometric evaluations: HINT-Q, HINT-N scores shall be recorded
- Audiometric evaluations in routine care shall be recorded, if available
- Objective measures: electrode impedances and ECAP shall be recorded
- Review of returned Subject's diary
- Subject shall be reminded about the correct use of Subject's diary
- New Subject's diary dispensed
- Complications/adverse effects shall be recorded
- Concomitant medication(s) shall be recorded

**Visit 7 (follow-up, Month +6 post-activation)**

- Audiometric evaluations: HINT-Q, HINT-N scores shall be recorded
- Audiometric evaluations in routine care shall be recorded, if available
- Objective measures: electrode impedances and ECAP shall be recorded
- Review of returned Subject's diary
- Subject shall be reminded about the correct use of Subject's diary
- New Subject's diary dispensed
- Complications/adverse effects shall be recorded
- Concomitant medication(s) shall be recorded

**Visit 8 (end of study, Month +12 post-activation)**

- Audiometric evaluations: HINT-Q, HINT-N
- Audiometric evaluations in routine care shall be recorded, if available
- Objective measures: electrode impedances and ECAP shall be recorded
- Review of returned Subject's diary
- Complications/adverse effects shall be recorded
- Concomitant medication(s) shall be recorded

**Unscheduled visit**

- Visit purpose shall be recorded
- Objectives measures: electrode impedance and ECAP, if available
- Complications/adverse effects shall be recorded
- Concomitant medication(s) shall be recorded

## **3.6 Study Outcome Evaluations**

### **3.6.1 Study Endpoints**

#### **3.6.1.1 Primary Endpoints**

Previous studies analyzed their samples based on fixed time intervals after implantation, usually 1, 3 and 6 months, then annually thereafter. After 6 months of CI experience outcomes appear to be stable with the majority of users reaching a performance plateau. Massa et al. [5] observed a performance plateau at a median of 4.7 months post-implantation. Similar results were reported by Bradley et al. [8] demonstrated a plateaued performance around 6 months in a sample of 55 patients. In Dillon et al. study [9] the adults tested with HINT in quiet at 70 dB experienced growth in speech perception within the first 6 months and remained stable thereafter. This plateau at 6

months is generally consistent with findings from others previous research with other speech discrimination tools, as Lenarz et al. study [7] using German language tests in a large cohort.

**a) HINT in Quiet (HINT-Q)**

The primary efficacy endpoint of the Neuro CIS is assessed with the HINT score in quiet in the ipsilateral ear. The primary endpoint is the difference between the baseline performance in the best-aided condition and the performance in the implanted ear within 6 months following activation. The mean score of words correctly repeated in quiet will be used as the primary outcome measure for assessing the primary benefit.

**b) Safety**

The occurrence of major complications within the first year of follow-up will be the co-primary endpoint for assessing the primary risk of device implantation.

Safety data shall be collected through the duration of the study and reflect the type and duration of any adverse event(s) and classified as major or minor complications. Evaluations shall be performed from baseline, during the operative time, and at each time points.

Three estimations of incidence rate will be provided:

- Major complications rate (co-primary estimate of device side-effects)
- Minor complications rate (secondary evaluation of side-effects).
- Incidence rate of any complications.

It is expected that major complication incidence rate will be within the range of variation of estimations obtained in previous studies on old generations of devices. A forest plot will present the estimate and 95% CI of incidence rate for the investigational device and estimates and 95% CI obtained in previous studies and previous generations.

**3.6.1.2 Secondary assessment criteria**

**a) HINT in quiet (HINT-Q) at month 3 and 12months**

The secondary endpoint is the score of words correctly repeated in quiet determined at 3, and 12 months post-activation in the implanted ear and the performances compared overtime.

**b) HINT in Noise (HINT-N)**

This efficacy secondary criterion is the score of words correctly repeated in noise preoperatively and at 3, 6 and 12 months post-activation in the implanted ear and the performances compare overtime.

**3.6.1.3 Other outcome of interest – Technical Functionalities**

The average of electrodes impedance values are collected at the different time points and observed over time.

The average of N1-P2 peaks amplitudes are determined at each time point and observed over time.

**3.6.1.4 Sample Size Determination**

Sample size determination is based on the two co-primary endpoints: change from baseline to 6 months of the HINT-Q (efficacy assessment), and major complication incidence rate during the 12 month follow-up (safety assessment).

The expected efficacy is an improvement of 50 points at 6 months of device use.

Change from baseline to 6 months is not available in literature, but 2 studies describe the HINT-Q magnitude after 12 months of device use. Waltzman et al. [42] described an increase of 47.7% (SD=26.6%) from pre- to 3 months post-implantation, similar results are reported by Lin et al. [43] with a magnitude of 60% (SD=24.1%) at 12 months. Considering an observed performance plateau around 6 months [5,8,9,7], we can consider that standard deviation obtained at 3 and 12 months can be used for 6 months of device use in this study. In addition in the main studies conducted at 6 months [5,6,8,9], the standard deviation are ranged from 22% to 28%, which is consistent with results change from baseline. Data from literature using the same efficacy assessment criterion provided a weighted average  $\pm$  weighted standard deviation change from baseline of 57.43%  $\pm$  25.05%.

Such estimation has been rounded conservatively to 50%  $\pm$  25%.

#### Sample size

The sample size required to have 95% chance to get a significant efficacy result assuming a true mean improvement of 50%, a standard deviation of change from baseline of 25% and a type I error of 0.025 (one-sided) is 7 patients. It means that the expected improvement is so large with respect to the variability that the sample size calculation is not driven by efficacy considerations.

As requested by the FDA, the sample size will be set at a total of at least 50 subjects to support the safety. If the incidence rate of major complications is 2% then the chance to observe at least one event is 63.5%. The exact upper limit of the 95% C.I. will be 10.6% for an observed rate of 2%. Regarding any complication the expected rate is 35%. If the observed rate is 36% then the precision is around 13% in points.

In order to ensure that at least 50 subjects will be implanted with the device, starting with the anesthesia followed by surgery procedure, 55 subjects will be included.

An arbitrary minimum of 39 English speaking patients and 16 non English speaking patients will be recruited to meet the FDA requirement. It is possible that the recruitment in a given language be smaller than expected. In this case patients from other languages may replace the shortage provided that a minimum of 5 French speaking patients and 5 Danish speaking patients be recruited to justify the class of language.

### 3.6.2 Outcome Data and Data Analysis

#### 3.6.2.1 Analysis Set

##### a) Full Analysis Set (FAS)

This set will include all subjects implanted with the device, regardless whether any post-operative data are available. The primary analysis will be performed on a subgroup of this set. This subgroup is composed of English speaking patients to avoid the probable effect of language on the response.

##### b) Per-Protocol Set (PPS)

This set of patients is composed of participants who complete the clinical trial according to the protocol.

It consists of subjects who satisfy the following criteria:

- Complete the pivotal study
- Protocol compliance during the pivotal study (complete post-implantation visits)
- No violation of any eligibility criteria that could influence the primary efficacy endpoint
- No violation of the protocol or deviation from the protocol which could influence the outcome of efficacy endpoints.

The type of protocol violation and protocol deviations that are considered to influence the outcome of the safety endpoints will be defined in the statistical analysis plan.

The English speaking subgroup in the PPS will be used in a sensitivity analysis of the primary analysis.

### **c) Safety Analysis Set (SAS)**

It consists of all subjects for whom surgery for implantation started.

#### **3.6.2.2 Analysis of Efficacy Endpoint(s)**

The primary analysis of the primary efficacy endpoint will be performed on a subgroup of the FAS which consists of all English speaking patients (Exclusion of Danish and French Canadian speaking patients). The primary test is a one sample T-test performed on the change from baseline to 6 months after activation of the device. The value of the mean improvement under the null hypothesis is zero. The type I error ( $\alpha$ ) is set to 0.025 (one-sided).

The one sample Wilcoxon rank test will be applied in a sensitivity analysis. In case the normality assumption is strongly violated or in the presence of several outliers the result of this sensitivity analysis will have a particular importance. The same analysis performed on the Per Protocol Set of patients in English speaking people will be another sensitivity analysis of the primary analysis.

#### **3.6.2.3 Co-primary Analysis of Safety Endpoint**

No formal hypothesis testing of safety data will be performed. The safety analysis consists of all enrolled subjects for whom implantation surgery was initiated. The incidence rate of major complications will be presented as well as its 95% exact confidence interval. A forest plot will present this rate with its 95% C.I. and the rates with the 95% C.I. of major complications in studies carried out with older generations of cochlear implants.

#### **3.6.2.4 Secondary analyses**

Claims for labeling will be based only on confirmatory results demonstrate through the primary analysis.

All secondary or sensitivity analyses are supportive estimates of effects related to the primary or secondary objectives.

##### **a) Time course of the HINT-Q response in the primary population**

The time course of the change from baseline in the HINT-Q will be estimated with a mixed model for repeated measures using the change from baseline as the response, the patients (random effect) and the visit (fixed effect) as covariates. The analysis will be done on the FAS subset of English speaking patients.

The time (visit) effect will be tested (H1: at least two visits differs on average) and if a significant effect of visits is observed then visits responsible for the significant difference will be searched. The 95% confidence interval of the mean at each visit will be provided.

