**c) Difference in the time course of HINT-Q responses across languages**

The FAS including all patients instead of the subset of English speaking patients will be used in these secondary analyses. A mixed model for repeated measures will be fitted using the change from baseline to M3, M6 and M12 in the HINT-Q score as the responses and the following covariates or terms: the visit (M3, M6 and M12, fixed effect), the patient (random effect), the language (fixed effect) and the interaction between visit and language. The variance covariance matrix will be unstructured. If the p value of the interaction is below 0.15 then a signal of potential interaction is detected and the time course of speech performance is possibly dependent upon the language. Regardless the p value of interaction a graph will present the time course of the response for each language.

A series of contrasts will be performed to estimate and test:

1) The difference between languages in the change from baseline at each time point.

The estimate and test at M6 will be the most supportive result.

2) The overall mean change from baseline at each time point. The test against no change will be performed. Results will be easily interpreted in the absence of potential interaction (No significant difference in the time course of response between the 3 languages).

3) The overall difference between M6 and M12 in the change from baseline to assess the sustainability of effect in the overall population. This estimate is interpretable in the absence of interaction between visit and language. In the presence of interaction the difference is not easily interpretable and sustainability will be estimated and tested in the English speaking patients only.

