## 3. General statistical approach

The quantitative variables will be summarized using the following parameters:

- Number of missing and non-missing data,
- Mean and Standard deviation,
- 2-sided 95% Confidence Interval (CI) of the mean,
- Median, minimum and maximum.

The qualitative variables will be summarized using the following parameters:

- Number of missing and non-missing data,
- Counts and percentages with 2-sided 95% CI.

Statistical analysis will be performed at the 5% global significance level using 2-sided tests.

Statistical tests will be chosen according the type of variable:

By default, missing data or unknown responses will not be counted in the denominator of percentages but will be presented in the results tables.

Handling of missing data:

- Rule 1: If the assessment at M6 is missing but a further assessment is available, the missing assessment will be replaced by the next available data.
- Rule 2: If the assessment at M6 and M12 are missing but the assessment at M3 is available then M3 score will be carried forward.
- Rule 3: If the assessment at M6 and M12 is not available in quiet conditions but available in noise then the score at M6 in noise will be used.
- Rule 4: In case of lost to follow-up or withdrawal of the informed consent for unknown reason a stochastic regression imputation will be used. This technique computes a regression equation that generates predicted values for the missing data. After a random error term generated from a normal distribution (with a mean of zero and a variance equal to the residual variance from the preceding regression analysis) is added to each predicted score and the resulting sum is used in place of missing values.
- Rule 5: In case of withdrawal not due to a failure of the implantation or complications the baseline will be imputed at month 6.
- Rule 6: In case of withdrawal due to major complications requiring new implantation, the worst observed score will be imputed.

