## **6.3. Analysis of secondary endpoints**

### **6.3.1. Time course of the HINT-Q response in FAS and PPS**

The analysis will be done on the FAS sub-group of English-speaking patients and replicated in PPS.

The time course of the change from baseline in the HINT-Q will be estimated with a mixed model for repeated measures using the change from baseline as the response, the patients (random effect) and the visit (fixed effect) as covariates.

The time (visit) effect will be tested (H1: at least two visits differ on average) and if a significant effect of visits is observed then visits responsible for the significant difference will be searched.

The intercept and its 95% confidence interval will be interpreted as the coverage effect of the implant over a period of one year. This will be an approximation due to the absence of an assessment at 9 months.

The 95% Confidence Interval of the mean at each visit will be provided.

(refer to table 10)

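### The English-speaking HINT-Q time-course model names no within-patient covariance; fitted literally it is compound symmetry, which could mildly miscalibrate its visit test and any follow-up visit contrasts

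*Protocol*

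**What the plan says.** Protocol 3.6.2.4 a) describes the English-speaking analysis as a "mixed model for repeated measures using the change from baseline as the response, the patients (random effect) and the visit (fixed effect) as covariates". SAP 6.3.1 keeps the same terms ("using the change from baseline as the response, the patients (random effect) and the visit (fixed effect) as covariates"). Neither text says anything about the residual covariance.

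The model has three outputs. The first is an overall test of visit. The second is a conditional follow-up: "if a significant effect of visits is observed then visits responsible for the significant difference will be searched". The third concerns estimation: "The 95% confidence interval of the mean at each visit will be provided". SAP section 3 sets the default level: "Statistical analysis will be performed at the 5% global significance level using 2-sided tests".

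For the all-language model, Protocol 3.6.2.4 c) and SAP 6.3.3 use the same response and the same random patient term, and add: "The variance covariance matrix will be unstructured".

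Two other places matter. Protocol 3.6.2.4 b) compares M6 with M12 in English speakers by a paired t-test. SAP 6.3.2 and Table 11.1 extend this to all three pairs of visits. Protocol 3.6.2.4 d) and SAP 6.3.4 carry the HINT-Q analyses over to HINT-N.

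**The concern.** A random patient intercept with independent, equal-variance residuals is compound symmetry. A programmer who follows a) or SAP 6.3.1 to the letter would fit that, and would fit something different for the all-language model.

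There is a reason to doubt equal correlations here. Protocol 3.6.1.1 cites a median time to plateau of 4.7 months after implantation. Under Protocol 3.5.6 the M3 visit falls 105-118 days after surgery, which is 3.5-3.9 months (days / 30.4). The M6 visit falls at 189-202 days, or 6.2-6.6 months. If that median carries over, about half the patients or more would still be rising at M3, and most would be stable by M6. Differences involving M3 would then vary more between patients than M6-M12 differences do.

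At stake is the calibration of a supportive description of growth and plateau. There is also a risk that the model and the paired t-tests give conflicting answers on the same visit pair in the same patients.

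**Working it through.** The documents give no figure for this model, so there is none to reproduce.

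**Inputs from the documents**
- n = 39 English speakers (Protocol 3.6.1.4).
- SD of change: 26.6 at 3 months, 24.1 at 12 months, and the planning value 25 for 6 months (Protocol 3.6.1.4).

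**Input assumed**
- Between-visit correlations. The worked case uses M3-M6 0.80, M6-M12 0.90 and M3-M12 0.70. Ranges follow below.

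**Step 1: true SD of each difference**, from Var = s1² + s2² - 2·r·s1·s2.
- M3-M6: 707.56 + 625.00 - 1064.00 = 268.56, SD 16.4
- M6-M12: 625.00 + 580.81 - 1084.50 = 121.31, SD 11.0
- M3-M12: 707.56 + 580.81 - 897.48 = 390.89, SD 19.8

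**Step 2: what compound symmetry uses.** With complete data the model applies the average of the three variances to every pair: (268.56 + 121.31 + 390.89) / 3 = 260.25, SD 16.1. The pooled standard error is 16.13 / √39 = 2.58.

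**Step 3: 95% half-widths.** The pooled value uses t = 1.992 on 76 df. The pair-specific value uses t = 2.024 on 38 df.

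| Difference | Pair-specific | Pooled |
|---|---|---|
| M3-M6 | 2.024 × 16.39/√39 = 5.3 | 1.992 × 2.58 = 5.1 |
| M3-M12 | 2.024 × 19.77/√39 = 6.4 | 5.1 |
| M6-M12 | 2.024 × 11.01/√39 = 3.6 | 5.1 |

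The M6-M12 interval is about 44% too wide (5.14 / 3.57). The M3-M12 interval is about 20% too narrow (5.14 / 6.41).

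**Step 4: error rates by simulation.** Each case had 40,000 trials, complete normal data and no true visit effect. The random-intercept model is the repeated-measures F test on 2 and 76 df. The unstructured comparator is Hotelling T².
- Worked case: overall visit test 6.4%. Unconditional pairwise error is 5.3% for M3-M6, 10.9% for M3-M12 and 0.5% for M6-M12.
- With the planned gate (pairs examined only after a significant visit test), M3-M12 error falls to about 6%.

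**Step 5: dependence on the assumed pattern.** Correlations are listed as M3-M6 / M3-M12 / M6-M12.

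| SD at M3/M6/M12 | Correlations | Overall test, random intercept | Unstructured |
|---|---|---|---|
| 25/25/25 | 0.8/0.8/0.8 | 5.2% | 5.1% |
| 28/25/22 | 0.8/0.8/0.8 | 5.1% | 5.0% |
| 25/25/25 | 0.8/0.64/0.8 | 5.8% | 5.0% |
| 25/25/25 | 0.7/0.7/0.9 | 6.1% | 4.9% |
| 26.6/25/24.1 | 0.7/0.7/0.9 | 6.4% | 4.8% |
| 28/22/22 | 0.7/0.7/0.9 | 6.7% | 5.0% |
| 28/22/22 | 0.5/0.5/0.95 (extreme) | 8.1% | 4.9% |

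In the fifth row, pooled 95% intervals cover 91.3% (M3-M6), 91.6% (M3-M12) and 99.7% (M6-M12). The intervals for the visit means are only slightly off: 94.1%, 95.3% and 96.2%. In the third row M3-M6 is not under-covered (97.2%), so the direction for that pair depends on the pattern.

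**The case against.** Several points on the other side stand.

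- **The plateau statement concerns means.** A reader might infer that the plan's own premise, scores that "experienced growth in speech perception within the first 6 months and remained stable thereafter", makes the visit test wrong. It does not. A rise and plateau in the mean is fitted by the fixed visit effect, and a shift shared by all patients leaves compound symmetry intact. Differing individual timing has to be added. The cited median and "After 6 months of CI experience outcomes appear to be stable with the majority of users reaching a performance plateau" make it plausible but do not establish it. On spread, Protocol 3.6.1.4 treats the SDs as transferable between visits.
- **The text does not say a random patient effect only.** It is silent on the residual matrix. Section c) lists the same random term together with an unstructured matrix, so the difference between a) and c) may be an omission rather than two opposing assumptions. The layout of SAP Table 10 does not settle it, because Table 12 for the unstructured model has the same layout.
- **The plateau is tested correctly elsewhere.** A reader might infer that the conclusion on sustainability rests on the pooled standard error. It does not. The paired t-tests in Protocol 3.6.2.4 b) and SAP 6.3.2 use each pair's own SD and hold about 5% (two-sided) in the simulated cases. The model itself promises intervals for visit means, not for differences.
- **The gate limits the damage under no visit effect.** The unconditional 10.9% for M3-M12 is not the rate at which the planned procedure errs. It would be about 6%.
- **The analysis is supportive.** Protocol 3.6.2.4 confines labeling claims to the primary analysis.

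What survives is this. If M3 truly differs, the gate opens as intended. The search then compares M6 with M12 using a standard error that is too large, beside a paired t-test on the same data that uses the right one.

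**Conclusion.** The point holds as a specification gap in a supportive analysis. Read literally, the English-speaking model is compound symmetry, while its all-language counterpart is unstructured.

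If M6 and M12 correlate more strongly with each other than with M3, the visit test runs at about 6-7% instead of 5% with 39 patients, and at about 8% in an extreme case. In the follow-up search the pooled standard error is too small for M3-M12, often too small for M3-M6, and too large for M6-M12. The model and the paired t-tests can then disagree.

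These sizes rest on assumed correlations, complete data and normality. With equal variances and correlations there is no harm. The primary M6 t-test, the paired sustainability t-tests and the labeling claims are unaffected.

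**What to change.** In Protocol 3.6.2.4 a) and SAP 6.3.1, state an unstructured within-patient covariance over M3, M6 and M12, fitted by REML with Kenward-Roger degrees of freedom and visit as a fixed effect. Take the visit test, the visit means with their confidence intervals and any follow-up visit contrasts from that model. Do the same for HINT-N.

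A random patient intercept is redundant beside an unstructured residual matrix. Drop it here and also in Protocol 3.6.2.4 c) and SAP 6.3.3, so that the sections match.

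The cost is one sentence and one programming statement. Three visits need six covariance parameters (three variances and three covariances), which about 39 patients can support. Little is lost if compound symmetry turns out to be true.
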